To assess colonization prevalence among PLWHA, we conducted an epidemiologic evaluation of MRSA among persons within the Johns Hopkins University AIDS Service (JHUAS). The study included 500 subjects (65.8 % male) along with the sexual partners of 35 subjects. The MRSA colonization prevalence was 16.8% among subjects and 37% (17/35) in their sexual partners (unpublished data). These findings demonstrate an exceptional difference in colonization prevalence in PLWHA compared to the US population¹⁰ and supports the need for further research to understand decolonization regimens that evaluate outcomes for individual decolonization only compared to the inclusion household and/or sexual partner interventions. We propose a randomized controlled trial (RCT) among 100 PLWHA (50 per arm) within the JHUAS to evaluate an individual versus household/sexual partner decolonization intervention.

2. Objectives/Aims

The specific aims of the proposed RCT are:

1. To compare a MRSA decolonization protocol for the colonized individual (index) versus the index plus their household member and/or routine sexual partner(s).
H0: Index plus household/sexual partner(s) decolonization will be associated with a lower occurrence of MRSA colonization at 6 months after completion of decolonization protocol.
2. To estimate the intervention effect size and develop an intervention fidelity assessment plan to scale the intervention into a larger multi-city R01 application.
3. To determine the molecular characteristics and antimicrobial susceptibilities of both the clinical and colonizing isolates among index patient as well as household members.

3. Background

Community-associated methicillin resistant *Staphylococcus aureus* (CA-MRSA) greatly impacts health outcomes among PLWHA. Outbreaks of CA-MRSA skin and soft tissue infections have occurred in metropolitan areas throughout the country including San Francisco¹¹, Boston¹² and Dallas¹³. These outbreaks have identified key risk differences for CA-MRSA colonization and/or infection among this population

Date: 6/10/13

Principal Investigator: [name], MPH, NP

Application Number: NA_00079147

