The applicant proposes a prospective, randomized controlled open-label trial known as SUSTAIN, or **Stop Community MRSA Colonization among Patients**. The SUSTAIN trial will evaluate MRSA decolonization and determine differences in the prevalence of MRSA colonization (main outcome) at 6 months. Patients with a known history of MRSA colonization will be recruited from the (JHUAS). After consent and baseline MRSA screening, index subjects (50 per arm), described below, will be randomized to a standardized decolonization protocol directed at both the individual and their household and/or sexual partner(s) or a decolonization for the individual alone. Each index (i.e. person living with HIV within the Johns Hopkins Moore Clinic) will be approached for enrollment in the study. Information flyers, study rotating digital kiosk and provider referral will be used for recruitment. We will also search the Johns Hopkins Hospital Epidemiology and Infection Control (HEIC) database for known MRSA colonized individuals and contact former study participants.

SUSTAIN Standardized Decolonization Regimen (intervention):

According to the IDSA clinical practice guideline⁷, the standardized decolonization regimen for the nose and groin will include a 5-day course of nasal mupirocin calcium 2% cream applied inside the nose twice daily, plus a 4% chlorhexidine gluconate (soap) used in the shower/bath every day for 10 days^{20,19}. For individuals colonized within the throat we will add chlorhexidine gluconate oral rinse 0.12% used in a gargle and spit fashion twice daily for 7 days. A standardized educational session on use and accompanying CDC instructional frequently asked questions handout and an instructional medication sheet will be provided. For children < 7 years of age, we will provide decolonization using 4% chlorhexidine gluconate (soap) used in the shower/bath every day for 10 days. No antimicrobial cream or gargle will be utilized. If an adult household member or sexual partner is colonized at a single site, he or she will receive the soap, rinse and Mupiricin cream. If he/she is not colonized at any body site, no decolonization regimen will be provided.

Date: 6/10/13

Principal Investigator: [name], MPH, NP

Application Number: NA_00079147

ENROLLMENT:

Patient Population/Setting:

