Randomization: This study has taken into consideration the guidelines for reporting of clinical trials as recommended by the CONSORT report²¹ to inform the study design (Figure 1). After recruitment and informed consent, patients will undergo pre-randomization screening. Patients who screen negative for MRSA at this point will have completed the protocol. Patients screening MRSA positive will then be randomized to the two possible open-label treatment arms. Arm 1 will include randomization to standardized decolonization protocol of the individual plus household and/or sexual partner(s). Arm 2 will include randomization to standardized decolonization protocol for the individual patient alone. Randomization will occur through computerized random number generation in Stata, version 11. A simple parallel randomization design will be utilized. Once developed, this randomization scheme will be placed in an individually concealed envelope. The RA will not be aware of the randomization scheme of the individual envelopes until opened in front of the patient on the day of randomization.

Figure 1: SUSTAIN Study Design Overview

* The household members and/or sexual contacts will be consented prior to initiation of the decolonization protocol

Data Collection Measures:

The risk factor questionnaire used in the proposed study has been thoroughly evaluated with over 1000 subjects (50% with HIV). Questions have been added or removed as applicable to this patient population. The

Date: 6/10/13

Principal Investigator: [name], MPH, NP

Application Number: NA_00079147

questions in the protocol can easily be administered by a study team member in 20 minutes. The questionnaire has been thoroughly evaluated by experts in the field of hospital epidemiology and infection control for content validity. In addition to the subject questionnaire, each instrument contains an additional section for the research team to interrogate the patient's medical record to verify specific pieces of the medical history such as CD4 count, medication history, viral load, etc. Adolescents will complete the questionnaire, but for children younger than 13, we will have the parent complete the risk factor questionnaire. Each document ends with a microbiology results page for the principle investigator (PI) to complete.

MRSA Screening Procedures:

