Dependent Variable (DV): The DV is a group of mutually exclusive, non-ordered outcomes which include: negative for *S. aureus*, positive for methicillin susceptible *S. aureus*, positive for methicillin resistant *S. aureus*.

Independent Variables: A thorough search of the available literature has been completed to develop the risk factor questionnaire designed for this study²³. The questionnaire includes: demographic data, medical history, sexual history, substance abuse history, as well as healthcare associated and community-based MRSA risk factors.

Sample Size: Based on prior studies, it appears that the probability of MRSA colonization at 6 months after decolonization ranges from 60% to 80%. Although an exact effect size is not known for individuals with household/sexual partner decolonization, we have considered both feasibility and public health importance. We believe the intervention will achieve a 50% reduction in colonization at 6 months (i.e. 30% colonization [0.30]

Date: 6/10/13

Principal Investigator: [name], MPH, NP

Application Number: NA_00079147

in the arm with individual and household/sexual partner decolonization compared to 60% [0.60] colonization in individual alone arm). **Based on these figures and an alpha of 0.05, the total sample size required to achieve approximately 80% power is 41 per arm.** We anticipate 20% attrition and will oversample by 9 subjects per arm, bringing total sample size to 50 per arm.

Statistical Analysis Plan: Demographic variables will be evaluated using chi-square and Fisher's exact testing as appropriate. Fisher's exact will also be utilized to compare proportion of persons colonized at 6 months. Multinomial logistic regression will be used to determine the odds of subsequent MRSA colonization in the two arms and to determine the magnitude of the effect size between the arms.

LIMITATIONS AND PLAN TO ADDRESS:

As with any clinical trial, this study has possible limitations:

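### Simple randomization is valid here, but stratifying on throat carriage and naming it as a covariate would be a cheap, optional gain in balance

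*Combined protocol and SAP*

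**What the plan says.** Section 4, ALLOCATION: Randomization, says "Randomization will occur through computerized random number generation in Stata, version 11" and "A simple parallel randomization design will be utilized"; then "this randomization scheme will be placed in an individually concealed envelope", opened in front of the patient. Blocks, strata and minimization are not mentioned anywhere.

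The allocation is described as equal. The opening of Section 4 says "index subjects (50 per arm), described below, will be randomized". Section 7, Sample Size, says "an alpha of 0.05, the total sample size required to achieve approximately 80% power is 41 per arm" and then "We anticipate 20% attrition and will oversample by 9 subjects per arm, bringing total sample size to 50 per arm".

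The sequence of events matters here. The throat is one of the sites swabbed at screening (Section 4, MRSA Screening Procedures). Randomization follows the culture results (Section 4, Study initiation after screening, and FOLLOW-UP). A positive throat culture adds an oral rinse to the regimen (Section 4, decolonization regimen, and Section 6). Having household members and/or a sexual partner is an eligibility condition (Section 5), and the risk questionnaire is completed at baseline.

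For analysis, Section 7 compares 6-month colonization by Fisher's exact test and plans a multinomial logistic regression for the size of the arm effect. Questionnaire domains are listed as independent variables, but the plan does not say which of them enter the model for the arm effect. Throat carriage is not named.

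**The concern.** An unrestricted list leaves two things to chance: the arm sizes and the mix of patients in each arm. With about 40 patients per arm expected to complete, an imbalance in a prognostic factor can shift the observed 6-month difference. Throat carriage is a natural candidate, because the plan itself treats these patients differently and their status is known at allocation. An unadjusted test does not remove such a shift, and the chi-square and Fisher comparisons planned for demographic variables would at most describe it. The estimate also has a second use: Aim 2 is to estimate the effect size for a larger multi-city application, so precision is worth having if it is cheap.

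**Working it through.** **Inputs from the documents.** 100 index patients; simple randomization; 60% versus 30% colonized at 6 months ("compared to 60% [0.60] colonization in individual alone arm"); alpha 0.05, taken as two-sided because the plan does not say; 20% attrition; Fisher's exact test.

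**Assumed inputs.** The documents give neither the prevalence q of throat carriage among MRSA-positive index patients nor its prognostic strength. I use q = 20% to 50%, and a shift in 6-month colonization of 10 to 30 points.

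**1. The plan's own figure.** The pooled normal formula is n = [1.96·√(2·0.45·0.55) + 0.842·√(0.60·0.40 + 0.30·0.70)]² / 0.30² = 41.97, so 42 per arm. The unpooled form gives 39.2, so 40. At 41 per arm the power of the uncorrected two-proportion test is 79.0%. The stated 41 is reproduced within rounding, and 41 + 9 = 50.

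**2. Arm sizes.** With X ~ Binomial(100, 0.5):
- P(X = 50) = 8.0%
- P(55/45 or worse) = 36.8%
- P(60/40 or worse) = 5.7%
- central 95% range for one arm: 40 to 60

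**3. Power cost of unequal arms.** After 20% attrition, a 60/40 split leaves 48 and 32. Exact Fisher power is 72.5% at 40/40, and 73.0% or 73.2% at 32/48, depending on which arm is larger. The slight rise comes from the discreteness of the test. For the uncorrected two-proportion test, power averaged over all simple-randomization splits is 77.6%, against 78.0% at 40/40. The cost is negligible.

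**4. Chance imbalance in throat carriage.** At 50 per arm the SD of the difference in prevalence is √(2q(1−q)/50): √(2·0.2·0.8/50) = 0.080 at q = 20%, and √(2·0.5·0.5/50) = 0.100 at q = 50%. In the normal approximation, P(difference > t) = 2[1 − Φ(t/SD)].

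| | q = 20% | q = 50% |
|---|---|---|
| more than 10 points | 21.1% | 31.7% |
| more than 15 points | 6.1% | 13.4% |

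Letting the arm sizes vary as they would under simple randomization gives nearly the same: about 21% to 32%, and 6.2% to 13.5%. With 40 completers per arm in place of 50, the same formula gives 26% to 37% and 9% to 18%.

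**5. Effect on the result.** Movement = imbalance × shift. For a 15-point imbalance, 0.15 × 0.10 = 1.5 points and 0.15 × 0.30 = 4.5 points, or 5% to 15% of the planned 30. The standard error at 40 per arm is √(0.60·0.40/40 + 0.30·0.70/40) = √0.01125 = 10.6 points. The movement is therefore about 0.14 to 0.42 standard errors. A typical movement is smaller: at q = 40% the SD is 0.098 and the median absolute imbalance 0.674 × 0.098 = 6.6 points, which gives 0.7 to 2.0 points.

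**6. After the change.** With two throat strata and blocks of at most 6, each stratum can end at most 3 patients apart, so the arms differ by at most 6 (53/47). Throat prevalence then differs by at most about 3/50 = 6 points at allocation.

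**The case against.** The case for leaving the plan alone is strong. Simple randomization is valid, and chance imbalance is part of the variability that the test already allows for. It is also the least predictable scheme, which has value in an open-label trial. Even the largest movement shown is under half a standard error and rests on two assumed inputs. The regression already planned could carry covariates without any change to the list. All of this stands, and it is why the point is optional.

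Three stronger readings are tempting but not supported.

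- A reader might infer that the trial will miss its design because it will not reach 50 per arm. Fifty is the expected allocation, and departures cost almost no power. Stratified blocks do not guarantee 50/50 either: with four strata and blocks of 4 and 6, the exact split occurs in only about 39% of trials and can reach 54/46.
- A reader might take the worst assumed combination (15-point imbalance, 30-point shift, unfavourable direction), in which the true gap seen by the test is 25.5 points and Fisher power at 40/40 falls from 72% to 57%. That figure is conditional on an uncommon draw and an assumed shift as large as the planned effect. It is not the trial's power.
- A reader might infer that contact structure must be a stratum. Only the index patient's reported situation is known at allocation. In Arm 1, contacts are screened after randomization, and adult contacts with no positive site receive no regimen. The extra treatment delivered therefore depends largely on consent and carriage found later. A factor that mainly governs how much Arm 1 delivers modifies the effect; imbalance in it confounds only if it also predicts outcome in Arm 2, which the documents do not show. The share with only a non-resident partner is not given, and that stratum could be nearly empty.

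**Conclusion.** The plan contains no error on this point. Its randomization is unbiased, and the 50-per-arm statement is reasonable as an expectation. What remains is a modest gain in balance and precision that the plan leaves unused: throat carriage is recorded before allocation, changes treatment, and enters neither the list nor a named analysis model. Under the assumed ranges, an imbalance of more than 15 points has a probability of about 6% to 14% and would move the arm difference by 1.5 to 4.5 points. The conclusion depends on throat carriage being prognostic. The documents make that plausible by giving carriers a different regimen, but they do not quantify it. If the shift is near 10 points or less, the benefit is small.

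**What to change.** In Section 4, ALLOCATION: Randomization, replace the simple list with permuted blocks of randomly varied, undisclosed size (for example 4 and 6), stratified by throat carriage at screening (yes/no).

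In Section 7, Statistical Analysis Plan, prespecify two baseline covariates in the logistic model that estimates the arm effect: throat carriage, and the index patient's reported contact type (household members versus non-resident partner only). Contact type is optional as a second stratum. The Fisher comparison can stay as written. It cannot include covariates, so the adjusted estimate should be declared alongside it. The adjustment also covers imbalance that arises through attrition, which stratified allocation cannot prevent.

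The cost is one new list from the same software, two sets of envelopes in place of one, and a sentence in the analysis plan. Sample size, visits and treatment are unchanged. The downside is slight predictability at the end of a block in an open-label trial, limited by varying the block sizes and not disclosing them.

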Individuals, 21 years of age and older, of all racial and ethnic groups, receiving care within the JHUAS who have a prior history of MRSA colonization are eligible to participate as the index HIV positive subject. This person should have at least two members in the household and/or a sexual partner. A post-consent pre-randomization screening phase will be completed to ensure subjects are MRSA colonized. In addition to these criteria subjects must be willing to be randomized to either arm of the study, including randomization to household and/or sexual partner evaluation. Sexual partners and/or household members will also be required to provide informed consent. Subjects and their contacts must have no documented or reported allergies to any agent used in the standardized decolonization regimen. Parental assent will be required for household members less than 7 years of age. Exclusion criteria include: allergy to any component of decolonization protocol; individuals who live alone and have no active sexual partners; individuals who are unable to provide written informed consent.

Recruitment Strategy:

Study team members will speak with JHUAS providers to discuss the study and seek patient referrals (i.e. index patient). A HIPAA waiver will be sought in order to obtain a list of patients with a known history of MRSA colonization from Johns Hopkins Hospital Epidemiology and Infection Control Department. In the HIPAA waiver, we are asking to contact the patient's provider in the Moore Clinic to inform of the patient's eligibility for the study prior to the subject seeing his or her provider in clinic. The provider could then inform the patient of their eligibility and ask if we can contact them about the study. [name] previous work has already identified over 70 JHUAS patients with a known history of MRSA colonization. The patients in this prior study have agreed to be contacted for future studies when they signed informed consent. We have included details for a HIPAA waiver to evaluate this information in this IRB application. We have also

Date: 6/10/13

Principal Investigator: [name], MPH, NP

Application Number: NA_00079147

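### No rule limits each household or couple to one index patient, so linked patients can be randomized separately; this dilutes the contrast, though only slightly unless several pairs enrol

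*Combined protocol and SAP*

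**What the plan says.** All references are to the combined protocol and SAP.

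- **Who may be an index patient (Section 5, Eligibility Criteria).** Patients of the one HIV service, aged 21 or older, with a history of MRSA colonization and with household members or a sexual partner, "are eligible to participate as the index HIV positive subject". The exclusions are allergy, living alone with no active partner, and inability to consent. None concerns a housemate or partner who is already enrolled.
- **Unit of randomization (Section 4, Allocation).** "Patients screening MRSA positive will then be randomized to the two possible open-label treatment arms". The design is simple parallel randomization of individuals.
- **What differs between arms (Section 4).** Every index patient is decolonized. Arm 1 extends this to household members and partners, with colonized adult contacts receiving the regimen; Arm 2 is for the index patient alone. Contacts in both arms are offered screening.
- **Recruitment (Section 4).** Sources are the clinic itself, provider referral and an infection-control database. Staff will also search for known carriers "and contact former study participants". The earlier study in this service enrolled 500 subjects "along with the sexual partners of 35 subjects" (text before Section 2).
- **Contacts (Sections 4 and 5).** Each index is asked to refer the primary partner. Contacts carry the index's study number with a household or partner suffix (HC or SP), for molecular linkage.
- **Analysis (Section 7).** Fisher's exact test compares colonization at 6 months. There is no term for linked subjects. Limitation 4 deals with contacts who cannot be reached, not with links between index patients.

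**The concern.** The arms differ in one thing only: whether the index patient's contacts are decolonized. That exposure belongs to a household or couple, but allocation is by individual. Two linked patients who both qualify can therefore be allocated separately, and simple randomization splits such a pair about half the time.

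When a pair is split, the Arm 2 member's housemate or partner is in an Arm 1 unit. If the two share a home, the other colonized household members are treated as well, so the Arm 2 patient receives in substance the Arm 1 exposure and is counted in Arm 2. Because every index patient is decolonized, even two linked patients both in Arm 2 each have one treated contact. All of this pulls the Arm 2 rate toward the Arm 1 rate.

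Linked patients in the same arm also share exposure and can recolonize each other, so their outcomes are correlated, while Fisher's test treats them as independent. Aim 2 is to estimate the effect size for a larger application, so any attenuation would carry into that design.

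**Working it through.** **Inputs (Section 7, Sample Size).** Colonization at 6 months of 0.30 in Arm 1 and 0.60 in Arm 2; alpha 0.05 (sidedness not stated, two-sided assumed); 41 evaluable per arm; 20% attrition; 50 randomized per arm. The number of linked pairs, k, is not in the documents and is varied as an assumption.

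**Step 1: reproduce the plan's figure.** The plan states: "Based on these figures and an alpha of 0.05, the total sample size required to achieve approximately 80% power is 41 per arm". With pooled variance and mean rate 0.45:

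n = [1.96·√(2·0.45·0.55) + 0.842·√(0.60·0.40 + 0.30·0.70)]² / 0.30² ≈ 42 per arm.

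Approximate power at 41 per arm is 79.0%. The stated figure reproduces to within one patient.

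**Step 2: baseline under the planned test.** With 20% attrition from 50, evaluable n = 50 × 0.80 = 40 per arm. Exact two-sided Fisher power for 0.60 vs 0.30 is 72.5% at 40 per arm and 74.5% at 41. This is the starting point with no linked pairs; that it lies below 80% is a separate matter.

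**Step 3: dilution model.** Of k pairs among 100 randomized, about k/2 are split, each placing one affected patient among the 50 in Arm 2. The affected share is f = (k/2)/50. Under full spill-over an affected patient has the Arm 1 risk, so the Arm 2 rate is 0.60 − 0.30f.

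| Linked pairs k | f | Arm 2 rate | Fisher power, 40 per arm | Chance of at least one split pair, 1 − 0.5^k |
|---|---|---|---|---|
| 0 | 0 | 0.600 | 72.5% | – |
| 1 | 1% | 0.597 | 71.5% | 50% |
| 2 | 2% | 0.594 | 70.6% | 75% |
| 5 | 5% | 0.585 | 67.6% | 97% |
| 10 | 10% | 0.570 | 62.4% | >99% |

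One or two pairs cost about 1 to 2 points, five pairs about 5, and ten pairs about 10. Ten pairs would mean that 20 of the 100 index patients are linked.

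**Step 4: how far the assumption matters.** Full spill-over is an upper bound for each split pair, because an Arm 2 patient may have other, untreated contacts. If an affected patient gains only half the benefit and 10% of Arm 2 is affected, the Arm 2 rate is 0.60 − 0.15 × 0.10 = 0.585 and power is 67.6% rather than 62.4%.

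In the other direction, about k/4 pairs fall wholly in Arm 2, adding k/2 patients who each have one treated contact. Counting these as fully affected too doubles f, so 5 pairs then give f = 10% and 62.4%. That is a looser bound, since nobody else in those households is treated.

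**Step 5: look for a rule elsewhere.** The HC/SP suffix identifies contacts but gives no instruction for a contact who is already an index. Neither the partner-referral text, Limitation 4 nor the analysis plan supplies one.

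**The case against.** The strongest reply is that linked index pairs may be rare. Both people must be 21 or older, in care at this service, have prior MRSA, be culture-positive at screening, and enrol separately. The documents give neither the HIV status nor the clinic status of the 35 subjects' partners, and the confidentiality provisions are written for partners who may not know the index's status. The re-contact pool is the more than 70 known carriers, not their partners. This stands: the documents show that linkage is possible, not that it is common.

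Three stronger readings are tempting and are not supported:

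- *The Arm 2 member's own household is always treated.* That holds only if the pair live together. For partners living apart, Arm 1 reaches the Arm 1 member's household and partner, and contacts who are not colonized receive nothing.
- *The arms will be materially contaminated.* A 5% or 10% affected share needs about 5 or 10 linked pairs together with full spill-over.
- *The damage cannot be addressed afterwards.* The exposure cannot be undone, but study numbers and the HC/SP suffix allow many linked patients to be identified and excluded in a sensitivity analysis. The plan simply does not call for one.

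Finally, Figure 1 and some pages are not available, so a rule could appear there. The point covers the visible text only.

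**Conclusion.** The gap is real. The visible eligibility, allocation and analysis sections let linked patients be randomized separately, and they neither prevent this nor account for it. The bias runs toward no difference, and the independence assumption behind the primary test fails for linked patients.

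The size is uncertain and probably modest. Under the assumptions of half of pairs split and full spill-over, one or two pairs cost about 1 to 2 points of power and ten pairs about 10. The result rests on the plan's own 0.60 and 0.30, 40 evaluable per arm, a two-sided test and an assumed number of pairs. It does not show that the trial will be contaminated to a damaging degree. It shows an avoidable risk to the trial's only contrast, worth closing before enrolment because the remedy is small.

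**What to change.** In Section 5, allow only one randomized index patient per household or primary-partner unit. Alternatively, where two linked patients are both eligible, randomize them as one unit and count one pre-specified member, the first enrolled, in the primary analysis.

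In Section 4, have staff check each new index patient against the index and HC/SP contact lists before randomization, without disclosing either person's status to the other. In Section 7, report the number of linked pairs and add a sensitivity analysis excluding them.

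The cost is a sentence or two of protocol text, one check per patient, and the loss of a few index patients from a limited pool (just over 70 known carriers from the earlier work, against 100 places). The protocol must also state how a second linked patient is handled when the first is in Arm 2. As Section 4 reads, contacts in that arm are offered screening, while decolonization is for the index patient alone. That is for the investigators to settle and write down; this review takes no position on it.
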